9.4 STUDY WITHDRAWAL CRITERIA

Patients will be withdrawn from the study if any of the following occurs;

- Patient withdraws consent
- Death

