11.2.2 TREATMENT DISCONTINUATION

Patients will be discontinued from the study treatment if any of the following occurs as noted in Section [9.5](#).

- Disease progression based on RECISTv1.1
- An inter-concurrent illness that prevents further administration of NOX66
- An adverse event that is intolerable to continue the treatment with NOX66 and doxorubicin or any DLT (Section [8.3](#)) that has not resolved to Grade 1.
- Any other reason the Investigator considered that impacts the patient's safety.

For the patients who discontinue treatment, they will continue on study for follow-up visits for tumor evaluation. All anti-cancer treatments should be recorded in the eCRF. In those patients who have evidence of disease progression during the combination of NOX66 and doxorubicin, additional tumor evaluation assessments are not needed.

If a patient is withdrawn from the study at any time, either at his/her request or at the Investigator's discretion, regardless of the reason, the Investigator will record on the relevant page of the eCRF the reason(s) for withdrawal and the day of last dosing. The eCRF (and the clinical study report) will include reasons for patient withdrawals, as well as other details relevant to the patient's withdrawal.

Any patient who appears to be noncompliant from Cycles 2 to 6 should be counselled but not withdrawn from the study. Patients who discontinue for non-safety related reasons or for noncompliance prior to the end of Cycle 1 in the Dose-Escalation Part can be replaced.

Should any patient withdraw or be withdrawn from the study prior to the completion of the Month 18 follow-up visit, every effort should be made to complete the assessments at the End of Study (Section [11.6.2.12](#)). Patients experiencing adverse events should be followed until the AE has resolved, stabilized, or is no longer deemed clinically significant, as judged by the Investigator. Appropriate supportive and/or definitive therapy will be administered as required.

Discontinuation due to treatment failure, as defined by disease progression, is to be expected since doxorubicin is not curative for sarcoma and the optimal dose and dose frequency is not known for NOX66. Alternate treatments for sarcoma may be offered to the patient.

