11.4.2.3 Cardiac Monitoring

A 12-lead ECG after 5 minutes of rest in the supine position will be obtained at Screening. In the Dose Escalation Cohort, triplicate 12-lead ECGs in close succession at least 1 minute apart will be obtained after 5 minutes of rest in the supine position at -0.75, -0.5 and -0.25 hours prior to administration of NOX66 and at 1, 2, 5, and 8 hours after the first dose of NOX66 monotherapy (Day 1).

On Day 7 of Monotherapy, 12-lead ECGs will be recorded performed in triplicate in the same manner and time points as on Day 1. In addition, Holter monitoring, will be conducted from 8 to 24 hours post NOX66. On Day 2 of Cycle 1, the same evaluation will be done before and after administration of NOX66, and Holter monitoring will be performed from 8 to 24 hours after NOX66 administration (Dose Escalation and Dose Expansion Cohorts). On Day 2 of Cycles 2 to 6, (combination of NOX66 and doxorubicin), triplicate 12-lead ECGs will be obtained after 5 minutes of rest in the supine position at -0.25 hours prior to and at 1, 2, 5 and 8 hours post morning dose of NOX66.

On days when serial ECG readings occur, before electrodes are removed after the initial reading, the electrode position is to be marked on the skin with indelible ink and the same electrode position used for all subsequent ECGs for each patient.

The following windows are acceptable for performing the ECGs:

- +/-5 minutes for pre-dose ECGs required at -0.75, -0.5 and -0.25 hours prior to NOX66 administration.
- +/-10 minutes for post-dose ECGs required at 1 hour and 2 hours after NOX66 administration.
- +/-15 minutes for post-dose ECGs required at 5 hours and 8 hours after NOX66 administration.

Echocardiography will be assessed at the start of Cycles 3, 5 and at the end of Cycle 6 (or Early Termination), and compared to baseline (Screening).

If clinically indicated, an additional echocardiograph will be done at Cycle 1 prior to the first dose of doxorubicin. All clinically significant findings that are not present at baseline should be reported as AEs.

Echocardiogram assessment can be performed 1 day prior to the scheduled visit day.

For any patient with an absolute decrease in LVEF of >10% from the previous evaluation, or if the actual LVEF decreases to ≤40%, or ≥ Grade 3 LV systolic dysfunction, doxorubicin must be discontinued and echocardiograms are to be performed at 6-month intervals in the post treatment phase.

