- On Day 1 review treatment log, collect unused study drug, assess compliance, from previous cycle.
- On Day 1, perform a physical examination (including weight, Section [11.4.2.2](#)).
- On Day 1 administer questionnaires BPI-SF, EORTC QLQ-C30, EORTC QLQ-FA12, and SAQ.

- On Day 1, collect urine and fasting blood samples for clinical laboratory tests prior to the first dose of NOX66 ([Table 3](#)). Prior to the start of the cycle, the patient must have a minimum ANC of $1000/\mu\text{L}^3$. On Days 9 and 16, obtain hematology and clinical chemistry values.
- On Day 1, dispense sufficient supply of study drug for 7 days administration.
- On Day 1, administer the appropriate number of NOX66 suppositories/per day per assigned dose cohort and instruct the patient to take the appropriate number of suppositories on Days 2-7.
- On Day 2, measure vital signs (blood pressure, pulse [radial or brachial (to be measured over 30 seconds if performed manually)], respiration rate and body temperature [oral or aural]; Section [11.4.2.1](#)) prior to the dose of doxorubicin.
- On Day 2, administer doxorubicin (75 mg/m^2) over 15 minutes (or as per standard of care) at approximately 1 hour after administration of NOX66.
- On Day 2, triplicate 12-lead ECGs will be obtained after 5 minutes of rest in the supine position at- 0.25 hours prior to and at 1, 2, 5, and 8 hours post morning dose of NOX66.
- On Day 2, PK samples are to be collected at pre-dose of NOX66 administration and at 4 hours post NOX66 administration and assayed for idronoxil and metabolites.
- On Day 2, PK samples are to be collected at 0.5 and 4 hours after the end of the doxorubicin infusion and assayed for doxorubicin and doxorubicinol.

The following assessments are required at Cycle 6 Day 21, or at Early Termination if the patient discontinues the study during the treatment period:

- Collect blood for BNP, troponin 1, immunoassays, cytokines, chemokines and genetic mutation,
- Assess tumor response with CT or MRI.
- Perform a physical examination (Section [11.4.2.2](#)).
- Measure vital signs (blood pressure, pulse [radial or brachial (to be measured over 30 seconds if performed manually)], respiration rate [to be measured over 60 seconds], and body temperature [oral or aural] (Section [11.4.2.1](#)).
- Collect urine and fasting blood samples for clinical laboratory tests (Section [11.4.2.4](#)).
- Administer questionnaires BPI-SF, EORTC QLQ-C30, EORTC QLQ-FA12 and SAQ.

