11. The additional tests for hematology and serum chemistry on Days 9 and 16 are to assess any hematological or clinical laboratory tests for DLTs and/or require a dose reduction to 60 mg/m^2 or lower (37.5 mg/m^2 or 18.75 mg/m^2 based on serum bilirubin), or a delay in initiation of another cycle of the combination. These additional hematological and clinical laboratory tests should be performed at each cycle. Visit windows are ± 2 days of the scheduled visit.
12. During combination treatment cycles, NOX66 is administered on Days 1 to 7 and doxorubicin is administered on Day 2.
13. Doxorubicin (75 mg/m^2 or reduced dose) to be given on Day 2 of each 21-day cycle.
14. For Dose-Escalation Cohorts, PK samples will be obtained at pre-dose and at 1 and 2 hours post NOX66 on Day 2 Cycle 1. PK samples for idronoxil will be obtained on Day 2 of Cycles 2, 4 and 6 at pre-dose and 4 hours post dose. Additional PK samples for idronoxil will also be obtained pre-dose on Day 7 and at 8 or 12 hours after the last dose of NOX66 on Day 7 for those on a TID or BID regimens, respectively on Cycles 1, 3, and 5. For the Dose Expansion Cohort, PK samples for idronoxil will be obtained on Day 2 of Cycles 1, 2, 4, and 6 at pre-dose and at 4 hours post NOX66 and on Cycle 1 at 6 hours post NOX66. On Cycles 1, 3, and 5 PK samples are to be collected just prior to the morning dose of NOX66 on Day 7. For doxorubicin in the Dose Escalation Cohort, PK samples will be obtained at 0.5, 4 and 6 hours after the end of infusion on Day 2 Cycle 1 and at 0.5 and 4 hours at the end of infusion on Day 2, Cycles 2, 4 and 6. For doxorubicin in the Dose Expansion Cohort, PK samples will be obtained at 0.5, 4 and 6 hours after the end of infusion on Day 2 Cycle 1 and at 0.5 and 4 hours at the end of infusion on Day 2, Cycles 2, 4 and 6 ([Table 7](#)).
15. All patients who discontinue the study early for whatever reason after the first dose of NOX66, or during treatment cycles (Cycles 1-6), will be followed up within 28 days of discontinuation and submit to assessments detailed in the column of Cycle 6 Day 21/Early Termination. Patients who discontinue the study early during the follow-up period will complete a final visit with assessments detailed in the column of End of Study/Early Termination. Patients who complete the study in full will have an End of Study visit at Month 18.
16. Adverse events to be recorded up to 30 days after the last dose of NOX66 or doxorubicin, whichever is longer.

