22.2.4 CHEMOKINES, CYTOKINES AND ENOX2

The laboratory that will assay the plasma samples for chemokines, cytokines and ENOX2 must use validated methods. The sampling times for collection of blood for pharmacodynamic variables are provided listed in [Table 9](#).

Table 9 Pharmacodynamic Sampling time Points

Assay	Blood Volume (mL)	Screening ^a	Day 7 Monotherapy	C3D1	C6D21/ET ^b
		Dose Escalation			
Chemokines and cytokines	1 X 4	X	X	X	X
Immuno assays and lipidomic assays	4 X 4	X	X	X	X
Genetic mutation	2 x 4	X	NA	NA	X
			Dose Expansion		
Chemokines and cytokines	1 X 4	X	NA	X	X
Immuno assays and lipidomic assays	4 X 4	X		X	X
Genetic mutation	2 x 4	X		NA	X

^aPharmacodynamic samples should be collected only after eligibility confirmation at Screening, or otherwise can be collected at Monotherapy Day 1/Cycle 1 Day 1 prior to the first NOX66 administration.

^b PD samples to be collected at Early Termination if the subject discontinues treatment prior to Cycle 6.

NA= not applicable; ET = Early Termination

The details on pharmacodynamic sample processing and shipping requirements will be provided in the Laboratory Manual.

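### The trigger for the Cycle 6 Day 21/Early Termination assessments is inconsistent, and on its main wording patients who stop both drugs but stay on study have no scheduled end-of-treatment safety tests

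*Combined protocol and SAP*

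**What the plan says.** Several parts of the protocol govern the visit that closes treatment.

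- **Visit text (11.6.2.9).** "The following assessments are required at Cycle 6 Day 21, or at Early Termination if the patient discontinues the study during the treatment period". The list covers BNP, troponin, biomarker and genetic samples, CT/MRI, physical examination, vital signs, laboratory tests, questionnaires and echocardiography.
- **Table 4, footnote 15.** "All patients who discontinue the study early for whatever reason after the first dose of NOX66", or during Cycles 1 to 6, are seen within 28 days and have the assessments in the Cycle 6 Day 21/ET column.
- **Study versus treatment.** Section 9.4 begins "Patients will be withdrawn from the study if any of the following occurs" and lists only withdrawal of consent and death. Section 9.5 lists progression, intercurrent illness, intolerable adverse events, unresolved DLTs and cardiac toxicity as reasons to withdraw treatment. Section 11.2.2 adds: "For the patients who discontinue treatment, they will continue on study for follow-up visits for tumor evaluation". It also mentions study withdrawal at the Investigator's discretion.
- **Biomarkers (Table 9, footnote b).** "PD samples to be collected at Early Termination if the subject discontinues treatment prior to Cycle 6".
- **Echocardiography.** The Cardiac Monitoring part of the synopsis ties the final echocardiogram to discontinuing before six cycles. Section 11.4.2.3 says only Early Termination, without defining it. It adds that, after a specified LVEF decline or Grade 3 or higher LV dysfunction, "echocardiograms are to be performed at 6-month intervals in the post treatment phase".
- **BNP and troponin (11.4.2.5).** Scheduled to the end of Cycle 6, with no early-stop time point.
- **Analysis (14.3.5, 14.3.8).** BNP and echocardiography are summarised at the end of Cycle 6 or Early Termination.

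**The concern.** The patients for whom an end-of-treatment safety assessment is most informative are those who stop early for toxicity or progression. On the wording of 11.6.2.9 and footnote 15 they do not trigger the visit, because they have stopped treatment and not left the study. On the wording of Table 9 they do trigger the part of it that collects biomarkers. Two sites could follow the protocol faithfully and collect different data.

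Echocardiographic change, BNP and troponin, laboratory tests, vital signs and physical findings are all primary endpoints in 11.1.1. If the visit is missed, it is missed selectively. The final BNP and echocardiography summaries would lean towards patients who tolerated six cycles without progressing, and would tend to make the combination look safer than it is.

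**Working it through.** The protocol states no figure for this point, so the check is a comparison of passages, then timing, then a rough count.

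**1. Trigger by location**

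| Place | What triggers the assessment |
|---|---|
| 11.6.2.9; Table 4 footnote 15 | Discontinuing the study |
| Synopsis, Radiological Imaging; 11.4.4 (CT/MRI) | Discontinuing from the trial |
| Synopsis, Cardiac Monitoring (echocardiogram) | Discontinuing before six cycles |
| Table 9 footnote b (pharmacodynamic and genetic samples) | Discontinuing treatment |
| 11.4.2.2, 11.4.2.3, 14.3.5, 14.3.8 | Early Termination, undefined |
| 11.4.2.5 (BNP, troponin) | End of Cycle 6 only |

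The term also names two visits. Section 11.2.2 sends anyone withdrawn from the study before Month 18 to the list in 11.6.2.12, which has no echocardiogram, BNP or troponin. Footnote 15 sends withdrawals during treatment to the Cycle 6 Day 21/ET column, which has all three.

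**2. What remains for a patient who stops both drugs and stays on study (literal 11.6.2.9 reading)**

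Months 6, 9 and 12 (11.6.2.10 and Table 4) contain CT/MRI, ECG, questionnaires, concomitant medications, adverse events and survival. Laboratory tests, vital signs and physical examination return only at Month 18. BNP and troponin do not return.

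Timing from Cycle 1 Day 1, with 21-day cycles and 30.4 days per month:
- Stop at the Cycle 2 scan: 42/30.4 = 1.4 months; 18 − 1.4 = 16.6 months to the next scheduled laboratory tests.
- Stop at the Cycle 4 scan: 84/30.4 = 2.8 months; 18 − 2.8 = 15.2 months.

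BNP is drawn on Day 1 of Cycles 1, 3 and 5, echocardiography is done on Day 1 of Cycles 3 and 5, and doxorubicin is given on Day 2. A patient who stops at the Cycle 2 scan therefore has no scheduled BNP after any doxorubicin on this reading, and an echocardiogram only if the site follows the synopsis or the patient meets the 11.4.2.3 cardiac criteria.

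**3. How many patients**

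Inputs: median PFS of 4.1 and 4.6 months (doxorubicin alone) and 6.6 and 7.4 months (combinations), from 6.1; 28 to 34 patients, from the synopsis; scans at the end of Cycles 2, 4 and 6. Assumption: exponential PFS counted from Cycle 1 Day 1. The Cycle 4 scan is the last one that can cause an early stop, because progression first seen on the Cycle 6 scan is found at the Cycle 6 Day 21 visit itself.

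P(progression by Day 84) = 1 − 2^(−2.76/median):
- 4.1 months: 0.37
- 4.6 months: 0.34
- 6.6 months: 0.25
- 7.4 months: 0.23

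Counts: 0.23 × 28 ≈ 6, and 0.37 × 34 ≈ 13.

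Toxicity stops come on top. In the ifosfamide study cited in 6.1, 3% (doxorubicin alone) to 18% (combination) could not complete six cycles because of adverse events.

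**The case against.** The strongest reply is that this is a loosely used term and not a missing visit. Section 11.6.2.12 itself speaks of patients who discontinue the study because of progression, so the authors may have meant footnote 15 to cover treatment stops. Its reach to any reason for discontinuing fits poorly with a trigger limited to death and withdrawn consent. The analysis sections plainly expect Early Termination values. This stands as evidence of intent, but not as an instruction a site can rely on: 9.4, 9.5 and 11.2.2 say something different, and 11.2.2 and footnote 15 point to different lists.

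The rest of the safety plan also limits the loss:
- Haematology and chemistry are drawn on Days 1, 9 and 16 of every cycle.
- Laboratory shift tables use the worst grade as well as the end-of-study grade.
- BNP and echocardiography are also summarised at Cycles 3 and 5.
- Cardiac Failure and Cardiomyopathy queries are summarised.
- Adverse events are recorded to 30 days after the last dose, clinically significant laboratory abnormalities are followed up, and extra visits are allowed.

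All of that stands. It softens the effect on adverse events and laboratory grades. It does not supply an end-of-treatment BNP, nor settle whether an echocardiogram is due.

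A reader might infer three stronger things that the documents do not support:
- **That early stoppers have no biomarker samples and no echocardiogram.** Table 9 footnote b requires the samples on stopping treatment, and the synopsis wording on the echocardiogram reads most naturally the same way.
- **That patients with LVEF decline are left out.** The cardiac rule stops doxorubicin. Under 10.2.3, NOX66 is to continue if doxorubicin stops after four cycles, and may continue if it stops earlier, so such patients can reach Cycle 6 Day 21. Section 11.4.2.3 also gives them six-monthly echocardiograms.
- **That 32% to 50% of patients would miss the visit.** The same formula gives that range at Day 126, but it counts progression first seen on the Cycle 6 scan.

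**Conclusion.** The inconsistency is real and should be corrected by amendment. The trigger is leaving the study in two places, stopping treatment in one, discontinuing before six cycles in another, and undefined elsewhere. Followed literally, 11.6.2.9 and footnote 15 leave patients who stop both drugs but remain on study without scheduled end-of-treatment BNP, troponin, laboratory tests, vital signs or physical examination, and with an echocardiogram that depends on the passage a site follows. The final BNP and echocardiography summaries would then mostly describe six-cycle completers.

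The group affected through progression is roughly 6 to 13 of 28 to 34 patients, plus toxicity stops. This rests on the exponential form, on PFS medians from other trials, and on sites applying the literal wording. If sites already treat a treatment stop as Early Termination and use the Cycle 6 Day 21/ET column, little is lost. The documents do not ensure that they will.

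**What to change.** Define one End of Treatment visit: Cycle 6 Day 21 or, if earlier, within footnote 15's existing 28 days of permanent discontinuation of all study treatment (both NOX66 and doxorubicin), for any reason and whether or not the patient stays on study. Naming both drugs matters because 10.2.3 lets NOX66 continue after doxorubicin stops.

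Bring into line with that definition:
- 11.6.2.9, and the Cycle 6 Day 21/ET column and footnote 15 of Table 4;
- the Cardiac Monitoring and Radiological Imaging parts of the synopsis;
- 11.4.2.2, 11.4.2.3 and 11.4.2.5 (adding the early-stop time point for BNP and troponin);
- Table 9 footnote b.

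Reserve End of Study/Early Termination for leaving follow-up, and correct the cross-reference in 11.2.2 and the progression wording in 11.6.2.12 to match. State whether the CT/MRI at this visit applies to patients whose progression is already documented, since 11.2.2 and 11.6.2.12 differ on it. In 14.3.5 and 14.3.8, summarise the End of Treatment value.

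Showing the six-monthly echocardiograms of 11.4.2.3 in Table 4 would be helpful but is optional.

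The cost is amendment wording and one visit of already planned assessments for each patient who stops early.

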11.6.2.10 Months 6, 9 and 12 (from Cycle 1 Day 1)

- Assess tumor response with CT or MRI.
- Single 12-lead ECG will be obtained after 5 minutes of rest in the supine position.
- Administer questionnaires BPI-SF, EORTC QLQ-C30 and EORTC QLQ-FA12.
- Review and record concomitant medications. Restrictions on concomitant medications are to be removed compared to NOX66 monotherapy and Cycles 1 to 6.
- Assess and review AEs (Section [16](#)).
- Assess overall survival.

11.6.2.11 Months 15 (from Cycle 1 Day 1)

- Conduct telephone follow-up or chart review.
- Assess and review AEs.
- Assess overall survival.

11.6.2.12 Month 18 (from Cycle 1 Day 1) - End of Study/Early Termination

- Assess tumor response with CT or MRI, including patients who discontinue the study for progressive disease.
- Measure vital signs (blood pressure, pulse [radial or brachial (to be measured over 30 seconds if performed manually)], respiration rate and body temperature [oral or aural]; Section 11.4.2.1).
- Assess ECOG performance status.
- Collect urine and fasting blood samples for clinical laboratory tests (Section 11.4.2.4).
- Administer questionnaires BPI-SF, EORTC QLQ-C30 and EORTC QLQ-FA12.
- Perform a physical examination (Section 11.4.2.2).
- Review and record concomitant medications.
- Assess and review TEAEs (Section 16).
- Assess overall survival.

Table 4 Schedule of Procedures and Assessments for Three Periods of the Study

Procedure/Assessment	Study Day	Dose Escalation & Dose Expansion	Dose Escalation NOX66 Monotherapy Period							
		Screening	Monotherapy (Days)							Off-treatment Days
		Day -28 to Day -1	1	2	3	4	5	6	7	8
Obtain informed consent		X								
Inclusion/exclusion criteria		X	X							
Medical and surgical history ¹ (including histopathology data and STS grade)		X	X							
Assess disease status (CT and/or MRI) ²		X								X
Vital signs ³		X	X						X	
Physical examination ⁴		X	X						X	
ECOG performance status		X							X	
Hematology, clinical chemistry ⁵		X	X						X	
Urine pregnancy test (WOCBP only)		X	X							
BNP, troponin I			X						X	
Blood for cytokines, chemokines, immunoassays (ENOX2)		X [†]	X [†]						X	
Genetic mutation sample		X [†]	X [†]							
Archival tissue sample (Optional)		X								
Urinalysis		X	X						X	
12-lead ECG ⁶		X	X						X	
Holter monitoring ⁶									X	
Dispense 7-day supply of NOX66			X							
Echocardiography		X								
Administer NOX66 ⁷			X	X	X	X	X	X		
PK samples ⁸			X	X					X	X
Record AEs		X						X		
Prior & concomitant medications		X						X		
Assess dosing compliance ⁹									X	
Brief Pain Inventory (BPI-SF) ¹⁰			X						X	
EORTC QLQ-C30 ¹⁰			X							
EORTC QLQ-FA12 ¹⁰			X						X	
Suppository Acceptance Questionnaire ^{10, 19}								X		

Procedure/Assessment Study Day	Dose Escalation and Dose Expansion Combination of Doxorubicin and NOX66 Treatment Period Cycles 1 - 3																
	Cycle 1 ¹						Cycle 2					Cycle 3					
	1	2	3-7	8	9 & 16	21	1	2	3-7	9 & 16	21	1	2	3-7	8	9 & 16	21
Assess disease status (CT and/or MRI) ²											X						
Vital signs		X						X					X				
Physical examination	X						X					X					
ECOG performance status																	
Hematology, clinical chemistry	X				X ¹¹		X			X ¹¹		X					X ¹¹
Urine pregnancy test (WOCBP only)	X*																
BNP, troponin I	X											X					
Blood for cytokines, chemokines, immunoassays (ENOX2)	X*, †											X					
Genetic mutation sample	X*, †																
Urinalysis	X						X					X					
12-lead ECG ⁶		X						X					X				
Holter monitoring ⁶		X															
Echocardiography	X ¹⁸											X					
Dispense 7-day supply of NOX66	X						X					X					
Administer NOX66 ¹²	X	X	X				X	X	X			X	X	X			
Administer doxorubicin ¹³		X						X					X				
PK samples ¹⁴		X	X	X [#]			X					X	X	X	X [#]		
Record AEs ¹⁶										X							
Prior and concomitant medications									X								
Collect unused medication, review patient log and assess compliance							X					X					
Brief Pain Inventory (BPI-SF) ¹⁹	X						X					X					
EORTC QLQ-C30 ¹⁹	X						X					X					
EORTC QLQ-FA12 ¹⁹	X						X					X					
Suppository Acceptance Questionnaire ^{10, 19}							X					X					
Overall survival																	

Dose Escalation and Dose Expansion
Combination of Doxorubicin and NOX66 Treatment Period Cycles 4-6

Procedure/Assessment	Dose Escalation and Dose Expansion															
	Cycle 4 ¹					Cycle 5					Cycle 6					
Study Day	1	2	3-7	9 & 16	21	1	2	3-7	8	9 & 16	21	1	2	3-7	9 & 16	21/ET ¹
Assess disease status (CT and/or MRI) ²					X											X
Vital signs			X					X						X		X
Physical examination	X					X						X				X
ECOG performance status						X										
Hematology, clinical chemistry	X			X ¹¹		X				X ¹¹		X			X	X
BNP, troponin I						X										X
Blood for cytokines, chemokines, immunoassays (ENOX2)																X
Genetic mutation sample																X
Urinalysis	X					X						X				X
12-lead ECG ⁶		X					X						X			
Holter monitoring ⁶																
Dispense 7-day supply of NOX66	X					X						X				
Echocardiography						X										X
Administer NOX66 ¹²	X	X	X			X	X	X				X	X	X		
Administer doxorubicin ¹³		X					X						X			
PK samples ¹⁴		X					X	X	X [#]				X			
Record AEs ¹⁶									X							
Prior and concomitant medications									X							
Collect unused medication review patient log and assess compliance	X					X						X				X
Brief Pain Inventory (BPI-SF) ¹⁹	X					X						X				X
EORTC QLQ-C30 ¹⁹	X					X						X				X
EORTC QLQ-FA12 ¹⁹	X					X						X				X
Suppository Acceptance ^{10, 19}	X					X						X				X
Overall survival																X

Abbreviations: BNP = brain type natriuretic peptide; CT = computed tomography; ECOG=Eastern Cooperative Oncology Group; ECG=electrocardiogram; ENOX2 = Ecto-NOX disulfide-thiol exchanger 2; EOS=End-of-Study; ET=Early Termination; Mo = month; MRI = magnetic resonance spectroscopy; PK=pharmacokinetics; QOL = Quality of Life; WOCBP = women of childbearing potential

Note: For days not specifically designated on the schedule of assessments, the standard of care for the individual institution will be followed, any AEs and concomitant medications will be recorded on the eCRF.

† Blood samples for chemokines, cytokines, immunoassays (ENOX2) and genetic mutation to be collected either after eligibility is confirmed at Screening, or on Day 1 just prior to the first dose of NOX66.

#Dose Escalation Cohort only

*Dose Expansion Cohort only

Dose Escalation and Dose Expansion Follow-Up Period and End of Study/Early Termination						
Assessment	Study Day	Follow-Up (months from Cycle 1 Day 1)				EOS/ET ¹⁵
		6	9	12	15 ¹⁷	
Assess disease status (CT and/or MRI) ²		X	X	X		X
Vital signs						X
Physical examination						X
ECOG performance status						X
Hematology						X
Clinical chemistry						X
Urinalysis						X
12-lead ECG		X	X	X		
Record AEs ¹⁷		X	X	X	X	X
Prior and concomitant medications		X	X	X	X	X
Brief Pain Inventory (BPI-SF) ¹⁹		X	X	X		X
EORTC QLQ-C30 ¹⁹		X	X	X		X
EORTC QLQ-FA12 ¹⁹		X	X	X		X
Overall survival		X	X	X	X	X

1. Full medical and surgical history will be recorded at Screening. At Day 1 monotherapy; an interim history is to be recorded prior to first dose of NOX66.
2. Standard of care imaging performed prior to informed consent but within 28-days of enrollment may be used to confirm screening requirements. Disease status will be measured by radiologic methods (CT or MRI) at Screening, prior to beginning of Cycle 1 (only for dose escalation, if the previous scan is more than 28 days), end of Cycles 2, 4 and 6, at Months 6, 9 and 12 and End of Study. No patient is permitted to start a subsequent cycle until it is confirmed that disease progression has not occurred at the scheduled imaging assessment timepoint.
3. Vital signs will include weight, body temperature, respiratory rate, radial pulse rates, and systolic and diastolic blood pressures. Height and body surface area will be recorded at Screening only.

4. Complete physical examinations will be conducted at Screening (Day -28 to Day -1), prior to the first dose of NOX66, at the start of each treatment cycle and at End of Study. Complete physical examinations will include examination of general appearance, skin, neck (including thyroid), eyes, nose, throat, heart, lungs, abdomen, lymph nodes, extremities, muscular skeletal and nervous system. Abbreviated physical examinations may be conducted as needed and will focus on new symptoms and will include examination of relevant systems as identified by the Investigator. Physical examinations need to include the assessment of the perineal and anal region.
5. Hematology and chemistry assessments will be done weekly during Cycle 1 and with a window of (± 2 days) during Cycle 2-6 and End of Study/Early Termination.
6. Refer to Table 8 for details. Triplicate 12-lead ECGs will be obtained after 5 minutes of rest in the supine position at -0.75, -0.5 and -0.25 hours prior to administration of NOX66 and at 1, 2, 5, and 8 hours after the NOX66 application on Monotherapy Days 1 and 7 (Dose Escalation patients only) and Cycle 1 Day 2 (all patients). Holter monitoring will be recorded from 8 to 24 hours post NOX66 on Monotherapy Day 7 and Cycle 1 Day 2. On Day 2 of Cycles 2 to 6, triplicate 12-lead ECGs will be obtained after 5 minutes of rest in the supine position at -0.25 hours prior to and at 1, 2, 5 and 8 hours post morning dose of NOX66.
7. Patients will receive instructions on how to use the suppository and receive an adequate number of dosage units for the assigned dose level. ANC must be $> 1000/\mu\text{L}^3$ prior to NOX66 administration.
8. In the NOX66 monotherapy, PK samples will be obtained on Day 1 at pre-dose (within 15 minutes of dosing) and at 1, 2, 3, 4, 6, 8, and 24 hours post application. On Day 7, PK samples will be collected at pre-dose (within 15 minutes prior to dosing) and at 1, 2, 3, 4, 6, and 8 hours post application as well as on Day 1 of the Washout Period at 8, or 12 hours after the last dose of NOX66 for those on a TID or BID regimens, respectively.
9. Dosing compliance for NOX66 will be assessed weekly. Days with an abnormally high number of bowel movements are to be noted in the eCRF.
10. Suppository Acceptance Questionnaire will be used to assess how acceptable the dosage form is to the patient.
11. The additional tests for hematology and serum chemistry on Days 9 and 16 are to assess any hematological or clinical laboratory tests for DLTs and/or require a dose reduction to 60 mg/m^2 or lower (37.5 mg/m^2 or 18.75 mg/m^2 based on serum bilirubin), or a delay in initiation of another cycle of the combination. These additional hematological and clinical laboratory tests should be performed at each cycle. Visit windows are ± 2 days of the scheduled visit.
12. During combination treatment cycles, NOX66 is administered on Days 1 to 7 and doxorubicin is administered on Day 2.
13. Doxorubicin (75 mg/m^2 or reduced dose) to be given on Day 2 of each 21-day cycle.
14. For Dose-Escalation Cohorts, PK samples will be obtained at pre-dose and at 1 and 2 hours post NOX66 on Day 2 Cycle 1. PK samples for idronoxil will be obtained on Day 2 of Cycles 2, 4 and 6 at pre-dose and 4 hours post dose. Additional PK samples for idronoxil will also be obtained pre-dose on Day 7 and at 8 or 12 hours after the last dose of NOX66 on Day 7 for those on a TID or BID regimens, respectively on Cycles 1, 3, and 5. For the Dose Expansion Cohort, PK samples for idronoxil will be obtained on Day 2 of Cycles 1, 2, 4, and 6 at pre-dose and at 4 hours post NOX66 and on Cycle 1 at 6 hours post NOX66. On Cycles 1, 3, and 5 PK samples are to be collected just prior to the morning dose of NOX66 on Day 7. For doxorubicin in the Dose Escalation Cohort, PK samples will be obtained at 0.5, 4 and 6 hours after the end of infusion on Day 2 Cycle 1 and at 0.5 and 4 hours at the end of infusion on Day 2, Cycles 2, 4 and 6. For doxorubicin in the Dose Expansion Cohort, PK samples will be obtained at 0.5, 4 and 6 hours after the end of infusion on Day 2 Cycle 1 and at 0.5 and 4 hours at the end of infusion on Day 2, Cycles 2, 4 and 6 ([Table 7](#)).
15. All patients who discontinue the study early for whatever reason after the first dose of NOX66, or during treatment cycles (Cycles 1-6), will be followed up within 28 days of discontinuation and submit to assessments detailed in the column of Cycle 6 Day 21/Early Termination. Patients who discontinue the study early during the follow-up period will complete a final visit with assessments detailed in the column of End of Study/Early Termination. Patients who complete the study in full will have an End of Study visit at Month 18.
16. Adverse events to be recorded up to 30 days after the last dose of NOX66 or doxorubicin, whichever is longer.
17. Month 15 will be telephone follow-up/chart review.
18. Echocardiography should be repeated prior to the first dose of doxorubicin if, after the first screening echocardiograph, a patient has clinical symptoms that may indicate worsening cardiac function.
19. Study Questionnaires (EORTC QLQ-C30, EORTC QLQ-FA12, BPI-SF and SAQ) to be administered if available in the required language.

